Note: the classification of potential adverse events and the examples presented below are based on purely theoretical considerations and/or published literature as there is no human experience with intrathecal rhHNS therapy to date.

POTENTIAL ADVERSE EVENTS: INTRATHECAL RHHNS

Adverse Events Due To Systemic Exposure To rhHNS

Although rhHNS is given intrathecally only, some proportion of the drug will diffuse from the CSF into the peripheral circulation. The resulting systemic exposure may cause events that are typically seen in patients receiving ERT via an intravenous administration, known as infusion-related reactions. An infusion-related reaction is defined as an adverse event that (1) begins either during or within 24 hours after the start of the infusion, and (2) is judged as possibly or probably related to study drug. Other AEs that occur prior to the infusion, along with AEs associated with protocol-defined testing and assessments (laboratory testing and physical examinations) that were performed prior to the infusion will not be defined as infusion-related reactions.

Adverse Events Related to the Direct Delivery of rhHNS to the CNS Through Intrathecal Administration

Examples of adverse events observed in other published clinical trials with intrathecally-administered peptides or proteins, include, but are not limited to the following: headache, fever, feeling of warmth, sensory parathesias (including feelings of warmth, tingling, or pain) or autonomic symptoms such as dry mouth or gustatory abnormalities (including loss of smell and metallic taste). Changes in mental cognitive status or level of consciousness that are not caused by pre-medication may either occur acutely or develop post-injection, over time.

Potential Adverse Events: IDDD -Related Adverse Events

Examples of adverse events related to the insertion or use of an IDDD include, but are not limited to, the following: catheter disconnection or fracture, erosion of portal/catheter through the skin, fibrin sheath formation around catheter tip, hematoma, implant rejection, malposition of catheter, migration of portal/catheter, occlusion of portal/catheter, portal site or subcutaneous tract infection, and sepsis.

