7.21.2.2 Serious Adverse Event

A serious AE (SAE) is any AE occurring at any dose that results in any of the following outcomes:

- Death
- Is life-threatening
- Requires inpatient hospitalization
- Requires prolongation of existing hospitalization
- A persistent or significant disability or incapacity

- A congenital anomaly or birth defect

Important medical events that may not result in death, be life-threatening, or require hospitalization may be considered an SAE when, based upon appropriate medical judgment, they may jeopardize the patient and may require medical or surgical intervention to prevent one of the outcomes listed in this definition. Examples of such medical events include allergic bronchospasm requiring intensive treatment in an emergency room or at home, blood dyscrasias or convulsions that do not result in inpatient hospitalization.

The National Cancer Institute Common Terminology Criteria for Adverse Events (CTCAE) Version 3.0 grading scale should be referenced when assessing the severity of an AE (see [Appendix 5](#)) If an AE is not described in the NCI CTC, the severity should be recorded based on the scale provided in Table 7-4. The severity of all AEs/SAEs should be recorded on the appropriate eCRF page as Grade 1, 2, 3, 4, or 5 corresponding, respectively, to a severity of mild, moderate, severe, life-threatening, or death.

Table 7-4 Adverse Event Severity

Severity	Definition
Grade 1 (Mild)	No limitation of usual activities.
Grade 2 (Moderate)	Some limitation of usual activities.
Grade 3 (Severe)	Inability to carry out usual activities.
Grade 4 (Life-threatening)	Immediate risk of death.
Grade 5 (Death related to an AE)	Death

Relationship of an adverse event or serious adverse event to study medication is to be determined by the Investigator based on the definitions in Table 7-5:

Table 7-5 Adverse Event Relatedness

Relationship to Product(s)	Definition
Not Related	Unrelated to study drug.
Possibly Related	A clinical event or laboratory abnormality with a reasonable time sequence to administration of study drug, but which could also be explained by concurrent disease or other drugs or chemicals.

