Probably Related	A clinical event or laboratory abnormality with a reasonable time sequence to administration of study drug, unlikely to be attributable to concurrent disease or other drugs and chemicals and which follows a clinically reasonable response on de-challenge. The association of the clinical event or laboratory abnormality must also have some biologic plausibility, at least on theoretical grounds.
Definitely related	The event follows a reasonable temporal sequence from administration of the medication, follows a known or suspected response pattern to the medication, is confirmed by improvement upon stopping the medication (dechallenge) and reappears upon repeated exposure (rechallenge).

Table 7-5 Adverse Event Relatedness

Relationship to Product(s)	Definition
	Note that this is not to be construed as requiring re-exposure of the patient to study drug; however, the determination of definitely related can only be used when recurrence of event is observed.

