7.21.3 Procedures for Recording and Reporting Adverse Events

7.21.3.1 Reporting Serious Adverse Events

Any SAE, regardless of relationship to study medication, which occurs in a patient after informed consent, should be recorded by the clinical site on an SAE form. The SAE must be completely described on the patient's eCRF, including the judgment of the Investigator as to the relationship of the SAE to the study drug or device. The Investigator will promptly supply all information identified and requested by the Sponsor (or contract research organization [CRO]) regarding the SAE.

The Investigator must report the SAE to the Shire Pharmacovigilance and Risk Management Department AND to the Shire HGT Medical Monitor on an SAE form. This form must be completed and FAXED within 24 hours of the Investigator's learning of the event to:

Shire Pharmacovigilance and Risk Management Department:

International FAX: [REDACTED] (UK) OR **United States FAX:** [REDACTED]

AND

Shire HGT Medical Monitor: [REDACTED] MD

[REDACTED]
FAX: [REDACTED] (USA)

Any follow-up information must also be completed on an SAE form and faxed to the same numbers listed above.

In the event of a severe and unexpected, fatal, or life-threatening SAE, the clinical site must contact the Shire HGT Medical Monitor by telephone; this is in addition to completing and transmitting the SAE form as stated above. The following provides contact information for the Shire HGT Medical Monitor.

If an SAE is assessed as severe and unexpected, or life-threatening, contact:

[REDACTED] MD
[REDACTED]
Shire Human Genetic Therapies, Inc.
[name]
[name]
Telephone: [REDACTED]
Fax: [REDACTED] (USA)
Mobile: [REDACTED]

The Investigator must promptly report all required information to the Institutional Review Board (IRB)/ Independent Ethics Committee (IEC). It is the responsibility of the Sponsor to ensure that each Investigator receives a copy of any CIOMS I/ MedWatch report that has been submitted to the appropriate regulatory agencies notifying them of an unexpected related SAE. The Investigator or Sponsor must ensure that the IRB/IEC receives a copy of the report and that a copy is also filed within their study files.

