7.21.3.2 Eliciting Adverse Events

Patients should be asked non-leading questions (eg, “How do you feel?”) and further questions should be posed if there is indication of an AE. The questioning should be conducted with due regard for objectivity and, in particular, the questioner should gather information regarding AEs from questioning the patient, the patient’s parent/guardian, spontaneous report by the patient or parent/guardian, laboratory reports, and any health care provider’s observations.

The onset date, resolution date, treatment administered, and outcome of each AE must be recorded on the appropriate eCRF. In addition, the relationship of each AE to study medication must be recorded.

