10.6 Efficacy, Safety, and Pharmacodynamic Evaluations

10.6.1 Primary Analyses

10.6.1.1 Safety Analysis

In general, safety assessments will be based on all assessments post-baseline. The assessment of safety will be based primarily on the frequency of treatment-emergent adverse events, due to study drug and on the frequency of clinically notable abnormal vital sign and laboratory values. Changes from baseline will be calculated by subtracting the baseline value from the post-baseline value.

All enrolled patients will be included in the safety analysis. Patients will be grouped according to the actual dose received.

No formal statistical test will be performed in the safety evaluations. Vital sign measurements, clinical chemistry, and hematology safety monitoring will be listed for each patient, and abnormal values will be flagged. These will also be summarized at each time point, including change from baseline.

Adverse events will be recorded throughout the study and at early termination. Adverse events and medical conditions will be coded using the Medical Dictionary for Regulatory Activities (MedDRA) Version 9.0 or later. In all cases (with the exception of device-related events), adverse event summaries will be based on all adverse event recorded beginning on Study Day 1 (treatment-emergent AEs).

Adverse events will be summarized by presenting, for each treatment group, the number and percentage of patients having any adverse event, having an adverse event in system organ class, and having each individual adverse event. Note that in any given category (eg, system organ class) a patient will only be counted once. In addition, those events which resulted in death or were otherwise classified as serious will be presented in a separate listing. The incidence of treatment-emergent adverse events (new or worsened from baseline) will be summarized by system organ class, severity, type of adverse event and relationship to trial medication.

Adverse events that occur up to 30 days after the last dose of study drug will be considered “on-treatment”. Adverse events which are deemed probably or possibly related to the device will be summarized by dose group and overall.

Laboratory data will be listed by patient and dose group. Patients with newly occurring abnormalities outside the normal range will be flagged and listed separately and summarized. Mean change from baseline values or shift tables will also be provided by dose group at each visit.

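### The infusion-related reaction definition and the device-related AE summary name only possibly and probably related events, leaving out the definitely related grade of Table 7-5

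*Protocol*

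**What the plan says.** The relatedness scale is in Section 7.21.2.2. The text that introduces Table 7-5 says: "Relationship of an adverse event or serious adverse event to study medication is to be determined by the Investigator". The table has four grades: Not Related, Possibly Related, Probably Related and Definitely related. The top grade requires that the event "is confirmed by improvement upon stopping the medication (dechallenge) and reappears upon repeated exposure (rechallenge", and a note adds that "the determination of definitely related can only be used when recurrence of event is observed".

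Two other places use relatedness as an inclusion rule:

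- Section 7.21.2.1 defines an infusion-related reaction by its timing and by a second condition, that the event "2) is judged as possibly or probably related to study drug".
- Section 10.6.1.1 plans the device output: "Adverse events which are deemed probably or possibly related to the device will be summarized by dose group and overall".

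On what is recorded, Section 7.21.3.2 says: "In addition, the relationship of each AE to study medication must be recorded". Section 7.21.3.1 asks for more, but only for serious events, "including the judgment of the Investigator as to the relationship of the SAE to the study drug or device". Section 7.21.2.1 also requires a causality assessment for every AE, without saying to what.

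Section 10.6.1.1 further states that treatment-emergent events "will be summarized by system organ class, severity, type of adverse event and relationship to trial medication", and Section 10 promises listings of all safety data.

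**The concern.** A rule meant to collect related events should take every grade above Not Related. Both rules stop one grade short, and the missing grade is the one with the strongest evidence of causality. Neither uses inclusive wording, such as at least possibly related, that would bring it back in.

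The primary objective is long-term safety of rhHNS given through a surgically implanted IDDD. The device sentence is the only planned summary by device causality, because the treatment-emergent table is split by relationship to medication. If its rule drops a grade, no other planned summary shows that grade for the device.

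A second gap lies upstream. The device summary covers all AEs, yet a judgement of relationship to the device is explicitly requested only for serious ones. An analysis plan can pool grades later, but it cannot recover a judgement that was never recorded.

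**Working it through.** The protocol states no figure on this point and safety is not formally tested, so the check compares passages.

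**Step 1. Grades named by each rule (original protocol and Amendment 1 agree).**

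| Grade in Table 7-5 | Infusion-related reaction, 7.21.2.1 | Device-related summary, 10.6.1.1 |
|---|---|---|
| Not Related | excluded, as intended | excluded, as intended |
| Possibly Related | named | named |
| Probably Related | named | named |
| Definitely related | not named | not named |

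Related grades on the scale: 3. Named by each rule: 2. Omitted by each: 3 − 2 = 1, the strongest.

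**Step 2. Do the rules use the Table 7-5 scale?** The infusion-reaction definition concerns study drug, which is what Table 7-5 grades, so the mismatch is direct. The device summary needs an assumption. Table 7-5 has a column headed for product(s), but its definitions are written for study drug or medication, and no separate device scale appears. The device half therefore holds if the same grades are used for the device.

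**Step 3. Can the omitted grade occur?** It needs recurrence. Injections are 28 days apart (Groups 1 and 2) or 14 days apart (Group 3), and Amendment 1 sets the study duration at 4 years. Recurrence on re-exposure is therefore attainable, although the grade may be rare. Suppose a reaction graded probably related recurs and is then graded definitely related. Read literally, the event so graded no longer meets the infusion-reaction definition. Stronger evidence of causality takes it out, which cannot be intended.

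**Step 4. Where do such events still appear?**

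- Definitely related to drug: in the overall AE tables, in the treatment-emergent table by relationship to trial medication, and in the listings.
- Definitely related to device: in the overall AE tables and the listings, but in no summary by device causality.
- Infusion-related reactions: Section 10 names no table of them, so this half is a faulty definition and not a faulty planned output.

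**Step 5. Is the device judgement collected?** For SAEs, yes (7.21.3.1). For other AEs, 7.21.3.2 names study medication only. The general causality requirement in 7.21.2.1 covers every AE but does not name the device.

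**The case against.** The strongest reply is that this is a wording slip with little effect. All events remain visible in the AE tables and listings, and no grade of drug relationship is excluded from the treatment-emergent table. The infusion-reaction text sits among issues to consider that the protocol calls theoretical, and no planned table depends on it. The scale is a drug scale: its top grade turns on stopping the medication, which fits a device poorly. Section 7.21.2.1 asks for causality on every AE and lists IDDD-related events as one of three classes, so the eCRF, which is not shown, may already hold a device field. Pooling of grades is also commonly settled in the SAP.

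Most of this limits the size of the point but does not remove it. An SAP that followed the stated rule would carry the omission forward, and the poor fit of the scale to the device is itself a reason to state one.

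Three stronger readings are tempting, and the documents do not support them:

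- A reader might infer that two planned summaries lose events. Only the device summary is planned.
- A reader might infer that recurrent mechanical faults, such as repeated port occlusion, are what the device table drops. The definitely related grade is worded for improvement on stopping the medication and return on re-exposure, so the text does not show that such faults would receive it.
- A reader might infer that one reclassified child moves a group's incidence by 25 percentage points (1 of 4). The protocol gives a maximum of 12 patients but no group sizes, so 4 per group is an assumption. Each patient is also counted once per category. Because the top grade requires recurrence, a child whose first occurrence was graded possibly or probably related is already counted, and omitting the later event then changes patient incidence by zero.

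**Conclusion.** The point stands in limited form. Against the protocol's own four-grade scale, both rules leave out the definitely related grade. For study drug this is a direct inconsistency in the infusion-related reaction definition. For the device it rests on the assumption that the Table 7-5 grades apply; if they do, the only planned summary by device causality omits the most certain cases. The missing explicit request for device relationship on non-serious AEs adds to the device half.

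The size is minor to moderate. The error lies in how events are classified, and no event is lost to the study. In particular, the documents do not support a claim that definitely drug-related harm is undercounted in the main safety tables. No numerical effect can be given, since it depends on how often the grade is used and on whether the same patient also has an event graded possibly or probably related.

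The conclusion covers the original protocol and Amendment 1. Whether Amendments 2 to 8 changed the wording cannot be checked in the text shown.

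**What to change.** 1. In Sections 7.21.2.1 and 10.6.1.1, name all three related grades (possibly, probably and definitely), or define both rules as any grade other than Not Related.
2. State which relatedness scale applies to the device. If it is Table 7-5, adapt the definitions so that they can be applied to a device.
3. In Section 7.21.3.2, require relationship to the device, as well as to study medication, for every AE and not only for SAEs.

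The cost is two wording corrections, a short statement of the device scale and, if it is not already there, one eCRF field. Counts of related events may rise slightly. Treatment and visits do not change.

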10.6.1.2 Clinical Laboratory Evaluations

Descriptive summaries of clinical laboratory evaluations (hematology, serum chemistry, urinalysis) results will be presented in summary tables by evaluation visit using number of patients (n), mean, median, standard deviation, minimum, and maximum. Changes from baseline will be summarized for each post-baseline visit. The number of patients with clinically significant laboratory results or abnormal results during the study period will be presented in shift tables.

For the laboratory measurements, shift tables will be presented in terms of Low (L), Normal (N), High (H), Missing (M). High and Low measurements will be based on reference ranges provided by the laboratory at the study site.

Clinical laboratory results will also be presented in data listings.

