7.7 Clinical Laboratory Tests

Blood, urine, and CSF samples will be collected as described below for clinical laboratory testing. Procedures for collection and handling of samples are included in the Laboratory and/or Study Operations Manual.

Patients will be in a seated or supine position during blood collection. Clinical laboratory tests will include hematology, serum chemistry, and urinalysis.

Laboratory Parameters

Clinical laboratory tests will be performed at a central laboratory include the following:

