7.7.3.1 Standard Urinalysis

The following urinalysis parameters will be performed at a central laboratory on urine samples:

- Macroscopic examination
- Microscopic examination of sediment
- pH

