7.7.4.1 CSF Cell Counts

An aliquot of each CSF sample collected will be evaluated for CSF standard chemistries, glucose, protein, and cell counts. These assessments will be performed at the local laboratory.

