11.11 Data Generation and Analysis

The clinical database will be developed and maintained by a contract research organization or an electronic data capture technology provider as designated by Shire HGT. Shire HGT or its designee will be responsible for performing study data management activities.

Adverse events will be coded using Medical Dictionary for Regulatory Activities (MedDRA) Version 9.0 or later. Concomitant medication will be coded using WHODRL. Centralized laboratories will be employed as described in the study manual to aid in consistent measurement of efficacy and safety parameters.

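### Section 10.6.1.2 takes High/Low limits from the study-site laboratory for tests that the protocol has run at a central laboratory, so values near a limit can be misclassified in the shift tables.

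*Protocol*

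**What the plan says.** Section 10.6.1.2 sits under 10.6.1 Primary Analyses. It opens: "Descriptive summaries of clinical laboratory evaluations (hematology, serum chemistry, urinalysis) results will be presented in summary tables by evaluation visit". It then plans shift tables with the categories Low, Normal, High and Missing, and fixes where the limits come from: "High and Low measurements will be based on reference ranges provided by the laboratory at the study site".

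The measurement sections name another laboratory for the same tests. Section 7.7 defines the group: "Clinical laboratory tests will include hematology, serum chemistry, and urinalysis". It introduces the parameter lists with "Clinical laboratory tests will be performed at a central laboratory include the following". Section 7.7.3.1 repeats this for urine: "The following urinalysis parameters will be performed at a central laboratory on urine samples". Section 11.11 gives the reason: "Centralized laboratories will be employed as described in the study manual to aid in consistent measurement of efficacy and safety parameters".

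The safety tests expressly assigned to a local laboratory are the CSF chemistries, glucose, protein and cell counts in section 7.7.4.1: "These assessments will be performed at the local laboratory". Section 10.6.1.2 does not name CSF among its tests.

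**The concern.** A reference range belongs to the method and laboratory that produced the result. Limits from another laboratory may rest on a different assay, instrument or reference population. Applying them to central results undoes part of what central testing is meant to achieve, because the measurement is common to all sites while the classification is not.

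The tables concerned serve the primary objective. Section 10.6.1.1 bases the safety assessment primarily on treatment-emergent adverse events and on the frequency of clinically notable abnormal vital signs and laboratory values. It also has new out-of-range laboratory findings flagged, listed and summarized. At most 12 patients in three dose groups are planned and safety data are not formally tested, so the tables will be read by eye and a single reclassified patient is visible.

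This is not a detail left open for the statistical analysis plan. The protocol states a rule, and the rule conflicts with its own measurement plan. An analysis plan that follows 10.6.1.2 inherits the mismatch; one that uses central ranges departs from the protocol.

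**Working it through.** There is no figure in the plan to reproduce. The check compares the sections and then works through what a mismatch does to a shift table.

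**Step 1: which laboratory runs the test, and whose limits classify it**

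| Test group | Run at | Limits under 10.6.1.2 |
|---|---|---|
| Hematology | Central (7.7) | Study site |
| Serum chemistry | Central (7.7) | Study site |
| Urinalysis | Central (7.7, 7.7.3.1) | Study site |
| CSF chemistry and cell counts | Local (7.7.4.1) | Not named in 10.6.1.2 |

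The three groups named in 10.6.1.2 are the three that 7.7 sends to the central laboratory. The sentence cannot be rescued by reading it as a rule for CSF. Even if CSF were included, the sentence would still govern the other three groups.

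**Step 2: which results are affected**

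Let C be the central upper limit and S the site upper limit for one parameter.

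- If S = C, no classification changes.
- If S < C, a value with S < x ≤ C is Normal by the central range and High by the site range. All other values keep their category.
- If S > C, a value with C < x ≤ S is High by the central range and Normal by the site range.
- Lower limits behave in the same way.

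Only values between the two limits are affected. With two sites whose limits S1 and S2 differ, a central result lying between S1 and S2 is High at one site and not at the other.

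**Step 3: what this does to a shift**

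Take S < C, baseline value b and later value x, with the site range used both times.

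- b ≤ S and S < x ≤ C: Normal to Normal becomes Normal to High, a false shift.
- S < b ≤ C and x > C: Normal to High becomes High to High, a hidden shift.
- Both values between S and C: Normal to Normal becomes High to High. The cell is wrong, but there is no false shift.

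The mismatch can therefore create shifts, hide them, or move a stable patient to another cell. Which of these happens, and how often, depends on S, C and the patients' values. The protocol gives none of these.

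**Step 4: what is not affected**

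Means, medians and changes from baseline use the measured values, not the limits. Adverse event tables do not use the Low/Normal/High categories. The values themselves are still listed by patient. The out-of-range flags in 10.6.1.1 would be affected if they use the same limits, which that section does not say.

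**The case against.** The strongest reply is that this is loose drafting with little practical effect. Section 11.7.1 requires laboratory documentation, including reference ranges, from the central or local laboratory as applicable, so central ranges should be on file. The presentations are to be detailed in an analysis plan that is not shown, and every result is listed. Section 10.6.1.1 speaks of clinically notable values, which need not mean every value outside a range, and it offers shift tables as an alternative to mean changes. All of this limits the consequence. None of it changes the sentence in 10.6.1.2, which does plan shift tables and names the site laboratory as the source of the limits.

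A reader might go further in three ways that the documents do not support:

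- **That the Low/Normal/High calls will be wrong.** No ranges are given, so nothing shows that site and central limits differ.
- **That a rate of extra High flags can be calculated.** Any such rate needs an assumed distance between the limits. A per-result flag rate also does not convert into a rate of false shifts when one range is used at baseline and afterwards, as step 3 shows.
- **That the error could pass for a dose effect.** The protocol gives neither the number of sites nor how the dose groups are spread over them, and no formal comparison of safety data is planned.

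**Conclusion.** The contradiction stands as written, both in the original protocol and in Amendment 1 of 27 January 2011. The supportable consequence is conditional: misclassification of near-limit results, and possible inconsistency between sites, in one family of primary safety tables. It rests on two assumptions: that the site and central ranges differ for at least some parameters, and that the analysis follows 10.6.1.2 literally. How many entries would change cannot be derived from the document. This is worth correcting, but it does not threaten the safety assessment as a whole.

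The cover lists amendments up to number 8 (1 February 2017). The text available contains only the original protocol and Amendment 1, so the sentence may already have been corrected.

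**What to change.** First check whether Amendments 2 to 8 still carry the sentence. If they do, replace it with: *High and Low will be based on the reference ranges of the laboratory that performed the test.* This means central ranges for hematology, serum chemistry and urinalysis, and the site laboratory's ranges only for the locally run CSF tests, if those are tabulated in this way.

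The cost is one sentence. No new data are needed, since section 11.7.1 already calls for the applicable laboratory's ranges.
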